3.4.6 Evaluating Adverse Experiences

An investigator, who is a qualified physician, will evaluate all adverse experiences according to the NCI CTCAE, version 4.0. Any adverse experiences which changes CTCAE grade over the course of a given episode will have each change of grade recorded on the adverse experience case report form.

All adverse events regardless of CTCAE grade must also be evaluated for seriousness.

Refer to [Table 3-4](#) for instructions in evaluating adverse experiences.

Table 3-4 An investigator who is a qualified physician, will evaluate all adverse experiences as to:

V 4.0 CTCAE Grading	Grade 1	Mild; asymptomatic or mild symptoms; clinical or diagnostic observations only; intervention not indicated
	Grade 2	Moderate; minimal, local or noninvasive intervention indicated; limiting age-appropriate instrumental ADL
	Grade 3	Severe or medically significant but not immediately life-threatening; hospitalization or prolongation of hospitalization indicated; disabling; limiting self care ADL.
	Grade 4	Life threatening consequences; urgent intervention indicated.
	Grade 5	Death related to AE.
	†Results in death; or †Is life threatening; or places the subject/patient, in the view of the investigator, at immediate risk of death from the experience as it occurred [Note: This does not include an adverse experience that, had it occurred in a more severe form, might have caused death.]; or †Results in a persistent or significant disability/incapacity (substantial disruption of one’s ability to conduct normal life functions); or †Results in or prolongs an existing inpatient hospitalization (hospitalization is defined as an inpatient admission, regardless of length of stay, even if the hospitalization is a precautionary measure for continued observation. (Note: Hospitalization [including hospitalization for an elective procedure] for a preexisting condition which has not worsened does not constitute a serious adverse experience.); or †Is a congenital anomaly/birth defect (in offspring of subject/patient taking the product regardless of time to diagnosis); or Is a new cancer; (that is a condition of the study) or Is an overdose (Whether accidental or intentional.) Any overdose whether or not associated with an adverse experience must be reported within 24 hours. Other important medical events that may not result in death, not be life threatening, or not require hospitalization may be considered a serious adverse experience when, based upon appropriate medical judgment, the event may jeopardize the subject/patient and may require medical or surgical intervention to prevent one of the outcomes listed previously (designated above by a †).	
Duration	Record the start and stop dates of the adverse experience. If less than 1 day, indicate the appropriate length of time and units	
Action taken	Did the adverse experience cause the test drug to be discontinued?	
Relationship to test drug	Did the test drug cause the adverse experience? The determination of the likelihood that the test drug caused the adverse experience will be provided by an investigator who is a qualified physician. The investigator’s signed/dated initials on the source document or worksheet that supports the causality noted on the AE form, ensures that a medically qualified assessment of causality was done. This initialed document must be retained for the required regulatory time frame. The criteria below are intended as reference guidelines to assist the investigator in assessing the likelihood of a relationship between the test drug and the adverse experience based upon the available information. The following components are to be used to assess the relationship between the test drug and the AE; the greater the correlation with the components and their respective elements (in number and/or intensity), the more likely the test drug caused the adverse experience (AE):	

Relationship to test drug (continued)	The following components are to be used to assess the relationship between the test drug and the AE: (continued)	
	Exposure	Is there evidence that the subject/patient was actually exposed to the test drug such as: reliable history, acceptable compliance assessment (pill count, diary, etc.), expected pharmacologic effect, or measurement of drug/metabolite in bodily specimen?
	Time Course	Did the AE follow in a reasonable temporal sequence from administration of the test drug? Is the time of onset of the AE compatible with a drug-induced effect?
	Likely Cause	Is the AE not reasonably explained by another etiology such as underlying disease, other drug(s)/vaccine(s), or other host or environmental factors
	Dechallenge	Was the dose of test drug discontinued or reduced? If yes, did the AE resolve or improve? If yes, this is a positive dechallenge. If no, this is a negative dechallenge. (Note: This criterion is not applicable if: (1) the AE resulted in death or permanent disability; (2) the AE resolved/improved despite continuation of the test drug; or (3) the study is a single-dose drug study.)
	Rechallenge	Was the subject/patient re-exposed to the test drug in this study? If yes, did the AE recur or worsen? If yes, this is a positive rechallenge. If no, this is a negative rechallenge. (Note: This criterion is not applicable if: (1) the initial AE resulted in death or permanent disability, or (2) the study is a single-dose drug study.) NOTE: IF A RECHALLENGE IS PLANNED FOR AN ADVERSE EVENT WHICH WAS SERIOUS AND WHICH MAY HAVE BEEN CAUSED BY THE TEST DRUG, OR IF REEXPOSURE TO THE TEST DRUG POSES ADDITIONAL POTENTIAL SIGNIFICANT RISK TO THE SUBJECT/PATIENT, THEN THE RECHALLENGE MUST BE APPROVED IN ADVANCE BY THE U.S. CLINICAL MONITOR AS PER DOSE MODIFICATION GUIDELINES IN THE PROTOCOL.
	Consistency with Study Drug Profile	Is the clinical/pathological presentation of the AE consistent with previous knowledge regarding the test drug or drug class pharmacology or toxicology?
The assessment of relationship will be reported on the case report forms /worksheets by an investigator who is a qualified physician according to his/her best clinical judgment, including consideration of the above elements.		

Record one of the following:		Use the following scale of criteria as guidance (not all criteria must be present to be indicative of a drug relationship).
Yes, there is a reasonable possibility of drug relationship.		There is evidence of exposure to the test drug. The temporal sequence of the AE onset relative to the administration of the test drug is reasonable. The AE is more likely explained by the test drug than by another cause. Depending on data collection method employed, drug relationship may be further graded as follows:
	Definitely related	There is evidence of exposure to the test drug. The temporal sequence of the AE onset relative to administration of the test drug is reasonable. The AE is more likely explained by the test drug than by another cause. Dechallenge is positive. Rechallenge (if feasible) is positive. The AE shows a pattern consistent with previous knowledge of the test drug or test drug class.
	Probably related	There is evidence of exposure to the test drug. The temporal sequence of the AE onset relative to administration of the test drug is reasonable. The AE is more likely explained by the test drug than by another cause. Dechallenge (if performed) is positive.
	Possibly related	There is evidence of exposure to the test drug. The temporal sequence of the AE onset relative to administration of the test drug is reasonable. The AE could have been due to another equally likely cause. Dechallenge (if performed) is positive.
No, there is not a reasonable possibility of drug relationship		Subject did not receive the test drug OR temporal sequence of the AE onset relative to administration of the test drug is not reasonable OR there is another obvious cause of the AE. (Also entered for a subject with overdose without an associated AE.) Depending on data collection method employed, drug relationship may be further graded as follows:
	Probably not related	There is evidence of exposure to the test drug. There is another more likely cause of the AE. Dechallenge (if performed) is negative or ambiguous. Rechallenge (if performed) is negative or ambiguous.
	Definitely not related	The subject/patient did not receive the test drug. OR Temporal sequence of the AE onset relative to administration of the test drug is not reasonable. OR There is another obvious cause of the AE.

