3.4.2 Recording Adverse Experiences

An adverse experience is defined as any unfavorable and unintended change in the structure, function, or chemistry of the body temporally associated with the use of the SPONSOR's product, whether or not considered related to the use of the product. Any worsening (i.e., any clinically significant adverse change in frequency and/or intensity) of a preexisting condition which is temporally associated with the use of the SPONSOR's product, is also an adverse experience.

Changes resulting from normal growth and development which do not vary significantly in frequency or severity from expected levels are not to be considered adverse experiences. Examples of this may include, but are not limited to, teething, typical crying in infants and children, and onset of menses or menopause occurring at a physiologically appropriate time.

Adverse events may occur during clinical trials, or as prescribed in clinical practice, from overdose (whether accidental or intentional), from abuse and from withdrawal.

Progression of the cancer under study is not considered an adverse event.

All adverse events that occur after the consent form is signed but before treatment allocation/randomization must be reported by the investigator if they cause the subject to be excluded from the trial, or are the result of a protocol-specified intervention, including but not limited to washout or discontinuation of usual therapy, diet, placebo treatment or a procedure.

From the time of treatment allocation/randomization through 30 days following cessation of treatment, all serious adverse events and drug related AEOSI must be reported by the investigator. Such events will be recorded at each examination on the Adverse Event case report forms/worksheets. The reporting timeframe for adverse events meeting any serious criteria is described in section 3.4.5.1. The investigator will make every attempt to follow all subjects with non-serious adverse events for outcome.

With Amendment 10, investigators are required to report drug related NSAEs if they meet criteria for AEOSI (refer to the *Pembrolizumab AEOSI Preferred Term List* document) or are ECIs described in Section 3.4.8 below. Previous ECI guidance is now updated in Amendment 10 and is no longer required to be reported to Merck safety group. Other NSAEs do not need to be reported.

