3.4.3.1 Reporting of Overdose to SPONSOR

If an adverse experience(s) is associated with (“results from”) the overdose of test drug or vaccine, the adverse experience(s) is reported as a serious adverse experience, even if no other criteria for serious are met.

If a dose of Sponsor's product or vaccine meeting the protocol definition of overdose is taken without any associated clinical symptoms or abnormal laboratory results, the overdose is reported as a non-serious Event of Clinical Interest (ECI), using the terminology “accidental or intentional overdose without adverse effect.

All reports of overdose with and without an adverse event must be reported by the investigator within 24 hours to the Sponsor either by electronic media or paper. Electronic reporting procedures can be found in the EDC data entry guidelines. Paper reporting procedures can be found in the Investigator Trial File Binder (or equivalent).

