3.4.5.1 Serious Adverse Experiences

A serious adverse event is any adverse event occurring at any dose or during any use of Sponsor's product that:

- Results in death;
- Is life threatening;
- Results in persistent or significant disability/incapacity;
- Results in or prolongs an existing inpatient hospitalization;
- Is a congenital anomaly/birth defect;
- Is an other important medical event

Note: In addition to the above criteria, adverse events meeting either of the below criteria, although not serious per ICH definition, are reportable to the Sponsor in the same timeframe as SAEs to meet certain local requirements. Therefore, these events are considered serious by the Sponsor for collection purposes.

- Is a new cancer (that is not a condition of the study);
- Is associated with an overdose.

Refer to [Table 3-4](#) for additional details regarding each of the above criteria.

For the time period beginning when the consent form is signed until treatment allocation/randomization, any serious adverse event, or follow up to a serious adverse event, including death due to any cause other than progression of the cancer under study (reference Section 3.4.5.1 for additional details), that occurs to any subject must be reported within 24 hours to the Sponsor if it causes the subject to be excluded from the trial, or is the result of a protocol-specified intervention, including but not limited to washout or discontinuation of usual therapy, diet, placebo treatment or a procedure.

For the time period beginning at treatment allocation/randomization through 90 days following cessation of treatment, or 30 days following cessation of treatment if the subject initiates new anticancer therapy, whichever is earlier, any serious adverse event, or follow up to a serious adverse event, including death due to any cause other than progression of the cancer under study (reference Section 3.4.5.1 for additional details), whether or not related to the Sponsor's product, must be reported within 24 hours to the Sponsor either by electronic media or paper. Electronic reporting procedures can be found in the EDC data entry guidelines. Paper reporting procedures can be found in the Investigator Trial File Binder (or equivalent)

Additionally, any serious adverse event, considered by an investigator who is a qualified physician to be related to the Sponsor's product that is brought to the attention of the

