3.4.9 Protocol-Specific Exceptions to Serious Experience Reporting

Efficacy endpoints outlined in this section will not be reported to the Sponsor as described in Section 3.4.5. Immediate Reporting of Adverse Experiences to the Sponsor except as follows:

- If a serious and unexpected adverse experience occurs for which there is evidence suggesting a causal relationship between the drug and the event, the event must also be reported as a serious and unexpected suspected adverse reaction within 24 hours to the Clinical Monitor either by electronic media or paper even if it is a component of the study endpoint (e.g., all-cause mortality).

Specifically, the suspected/actual events (as opposed to endpoints or endpoint components) covered in this exception are as follows: hospitalization or death due to progression of the cancer under study if the events are considered drug related. Note: As described in Section 3.4.5.1, any secondary primary cancer needs to be reported as an SAE.

For this protocol, the Following MedDRA Preferred Terms are considered suspected efficacy endpoint/endpoint events:

- Disease Progression
- Malignant Neoplasm Progression

The Sponsor will monitor unblinded aggregated efficacy endpoint event and other safety data including fatal events to ensure the safety of the subjects in the trial. Any suspected endpoint which upon review is not progression of the cancer under study will be forwarded to global safety as a SAE within 24 hours of determination that the event is not progression of the cancer under study.

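### Table 3-4, which sites are told to use to judge seriousness, contradicts the rest of the safety section on new cancers and on overdose

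*Combined protocol and SAP*

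**What the plan says.** Section 3.4.5.1 lists the standard seriousness criteria and adds two that the sponsor treats as serious for collection purposes. One is a further malignancy, "Is a new cancer (that is not a condition of the study". The other is an adverse event that "Is associated with an overdose". It then refers the reader to Table 3-4 for detail on every criterion. Section 3.4.6 requires each adverse event to be assessed for seriousness and names the same table as the instructions.

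In that table the two added criteria read differently. The first is "Is a new cancer; (that is a condition of the study". The second is "Is an overdose (Whether accidental or intentional.) Any overdose whether or not associated with an adverse experience must be reported within 24 hours".

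Other parts of the safety section bear on both:

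- Section 3.4.9, citing 3.4.5.1, says that "any secondary primary cancer needs to be reported as an SAE".
- Section 3.4.2 says: "Progression of the cancer under study is not considered an adverse event".
- Section 3.4.3.1 makes an adverse experience that results from an overdose serious. With no symptoms and no laboratory abnormality, "the overdose is reported as a non-serious Event of Clinical Interest (ECI".
- Section 3.4.8 puts that symptom-free overdose first in its list of ECIs.

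Section 3.4.2 also fixes what the grading decides. Since Amendment 10, a non-serious event has to be reported only if it is a drug-related adverse event of special interest (AEOSI) or an ECI.

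**The concern.** The table is the working tool for grading, and nothing says which wording prevails when it disagrees with the text. On new cancers it states the reverse of the criterion it is meant to explain. On overdose it makes serious an event that two other sections call non-serious.

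The consequences differ. Seriousness now decides whether many events are collected at all, so a wrong grade for a second primary could mean a missing record. For overdose, a wrong grade means that the same event counts as an SAE at one site and as an ECI at another. Both would affect the safety summaries planned in 3.5.5.5. Neither affects response, progression or survival analyses.

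**Working it through.** No arithmetic underlies the point. The check is to classify the same event under each section.

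| Event | 3.4.5.1 | 3.4.9 | 3.4.3.1 and 3.4.8 | Table 3-4 as printed |
|---|---|---|---|---|
| Second primary that is neither carcinoma nor melanoma (for example a hematologic malignancy) | Serious | SAE | Silent | Not met by the new-cancer line |
| Carcinoma arising in a melanoma patient, study condition read as the patient's own cancer | Serious | SAE | Silent | Not met by the new-cancer line |
| The same, study condition read as any tumor the protocol admits | Not met by the new-cancer line | SAE | Silent | Serious |
| Overdose with an associated adverse event | Serious | Silent | Serious | Serious |
| Overdose with no symptoms or laboratory abnormality | Not met | Silent | Non-serious ECI | Serious |

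**New cancer.** In all three second-primary rows, 3.4.5.1 and the table give opposite answers. The third row arises because Part A admits any carcinoma. Only 3.4.9 gives one answer throughout.

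**What follows from a non-serious grade.** Take a second primary judged unrelated to drug and managed without admission. It is not an ECI, since 3.4.8 lists only symptom-free overdose and a liver-test pattern. It is not a drug-related AEOSI. If the table's new-cancer line is not met, the remaining route to serious is the important-medical-event clause, which is a matter of judgment. What happens next depends on timing:

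- Up to the 30-day Safety Follow-up Visit, 3.4.2 does not require a report. Section 3.2.5.4.6 and the follow-up flow-chart footnotes ask for all adverse events. The outcome depends on which text the site follows.
- From day 30 to day 90, a span of 90 − 30 = 60 days, the flow charts collect SAEs and drug-related events. An unrelated second primary is collected only if graded serious. Under 3.4.5.1 this window closes at 30 days if new anticancer therapy starts.
- After day 90, 3.4.5.1 asks only for SAEs judged related, so the table's wording makes no difference to an unrelated event.

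**Overdose.** The conflict is confined to the last row. Sections 3.4.3.1 and 3.4.8 and the table all ask for a report within 24 hours, although the closing sentence of 3.4.8 also tolerates the next working day. The event is therefore reported under any reading, and only its label changes.

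**Currency of the text.** The change summary records deletion of a Table 3-4, but that was the former AEOSI list. The seriousness table is current text.

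**The case against.** The strongest reply is that the right rule for second primaries stands in two other places. A site would have to work from the table, disregard the list in 3.4.5.1 that sent it there, and disregard 3.4.9. It would then have to find no hospitalization and decline to call a new malignancy an important medical event. This stands as a limit on likelihood: loss is a risk and not a certainty. It does not remove the contradiction, because the text itself directs sites to the table.

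A reader might infer more than the documents support:

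- **That the table captures no second primaries and the text captures all.** Part A takes any carcinoma, so a second carcinoma can literally be a condition of the study. It would then meet the table's line and fail the wording of 3.4.5.1.
- **That a missed second primary would never be recorded.** Section 3.2.5.4.6 and the flow charts ask for all adverse events up to the 30-day visit.
- **That progression of the study cancer would swell the SAE counts.** The table grades adverse experiences. Section 3.4.2 says that progression is not one, and 3.4.9 repeats the exception, so progression should not reach the table.
- **That all 1260 enrolled patients are exposed.** The reduced reporting dates from Amendment 10, which concerns patients still in the study then. Their number is not given.

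It can also be said that overdose records should be rare. The definition is at least 1000 mg above the prescribed dose, which with 50 mg vials is 1000 / 50 = 20 extra vials. That is fair, and the documents show no such record.

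Finally, the new-cancer conflict rests on one short word. If the reader's copy of the table prints the negation, that half of the point falls. The overdose half does not depend on it.

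**Conclusion.** The point holds as an internal contradiction in an operative safety rule, and it should be corrected. On both sponsor-added criteria, Table 3-4 disagrees with the sections it serves. For new cancers there is a limited risk that a second primary that is unrelated and managed without admission goes unreported. That risk is clearest in the 60 days after the 30-day visit, and is possible earlier where a site follows 3.4.2 and not 3.2.5.4.6. For overdose the effect is SAE versus ECI misclassification, with no loss of reports.

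The conclusion assumes that some sites grade from the table, as instructed. The documents give no rate of second primaries or overdoses, so no count of affected patients can be offered. No efficacy endpoint, test or power statement depends on it.

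**What to change.** Reconcile Table 3-4 with 3.4.5.1, 3.4.9, 3.4.3.1 and 3.4.8, so that each criterion has one wording:

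1. In the new-cancer line, put in the missing negation. Better, use the rule of 3.4.9 in both the table and 3.4.5.1: any second primary cancer, as distinct from progression of the patient's own cancer under study. Adding the negation alone would keep a phrase that is ambiguous when Part A admits any carcinoma.
2. Replace the overdose line with "Is associated with an overdose", and add a pointer to 3.4.3.1 for overdose without symptoms, keeping the 24-hour reporting requirement.
3. Before the next database lock, check that second primaries and overdoses already recorded follow the single rule, and recode any that do not.

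The cost is two table lines, a matching phrase in 3.4.5.1 if the better wording is adopted, notice to sites through the next amendment, and a short review of existing records. No planned analysis changes.
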